7.1.7. Additional Analysis of Adverse Events

7.1.7.1. Stage 3 Opportunistic Illnesses in HIV

On an ongoing basis, AEs will be reviewed for events that might meet the definition of stage 3 opportunistic illnesses in HIV that are indicative of an AIDS-defining diagnoses (see Protocol Appendix 6). The Gilead medical monitor will review the possible stage 3 opportunistic illnesses and approve the events that meet the definition. Events that meet the stage 3 opportunistic illness definition of an AIDS-Defining Diagnosis will be listed.

7.1.7.2. Cardiovascular or Cerebrovascular Events

Preferred terms for cardiovascular or cerebrovascular events are from relevant Standardised MedDRA Query (SMQ). The selected PT listing was provided by Gilead GLPS and reviewed by Gilead medical monitors (see details in [Appendix 3](#)).

The number and percentage of participants with treatment-emergent cardiovascular or cerebrovascular events and serious cardiovascular or cerebrovascular events by PT will be summarized by treatment group (B/F/TAF, Delayed Switch to B/F/TAF, and All B/F/TAF) based on the B/F/TAF safety analysis set. A by-subject data listing of cardiovascular or cerebrovascular events will be provided.

7.1.7.3. Hepatic Events

Preferred terms for hepatic events are from 15 relevant SMQs, which are identified as non-infectious and non-congenital hepatobiliary disorders. The selected PT listing was provided by Gilead GLPS and reviewed by Gilead medical monitors (see details in [Appendix 4](#)).

The number and percentage of participants with treatment-emergent hepatic events and serious hepatic events by PT will be summarized by treatment group (B/F/TAF, Delayed Switch to B/F/TAF, and All B/F/TAF) based on the B/F/TAF safety analysis set. A by-subject data listing of hepatic events will be provided.

7.2. Laboratory Evaluations

Laboratory data collected during the study will be analyzed and summarized using both quantitative and qualitative methods. Summaries of laboratory data will be provided for the B/F/TAF safety analysis set and will include data collected up to the last dose of B/F/TAF study drug plus 30 days.

The analysis will be based on values reported in conventional units. When values are below the LOQ, they will be listed as such, and the imputed value will be used for the purpose of calculating summary statistics as specified in Section 3.7.

A by-subject listing for laboratory test results will be provided by subject ID number and visit in chronological order for hematology, serum chemistry, and urinalysis separately. Values falling outside of the reference range and/or having a severity grade of 1 or higher on the Gilead Grading Scale for Severity of Adverse Events and Laboratory Abnormalities will be flagged in the data listings, as appropriate.

7.2.1. Summaries of Numeric Laboratory Results

Descriptive statistics will be provided by treatment group (B/F/TAF, Delayed Switch to B/F/TAF) for each laboratory test specified in the study protocol as follows:

- Baseline values
- Values at each postbaseline analysis window
- Change from baseline at each postbaseline analysis window

A baseline laboratory value will be defined as the last nonmissing value obtained on or prior to the date of first dose of study drug. Change from baseline to a postbaseline visit will be defined as the postbaseline value minus the baseline value. The mean, median, Q1, Q3, minimum, and maximum values will be displayed to the reported number of digits; SD values will be displayed to the reported number of digits plus 1.

In the case of multiple values in an analysis window, data will be selected for analysis as described in Section 3.8.3.

Calcium Corrected for Albumin

Calcium corrected for albumin will be calculated and summarized for the study. The following formula will be used when both serum calcium and albumin results for a given blood drawn are available and serum albumin value is < 4.0 g/dL.

- Calcium corrected for albumin (mg/dL) = serum calcium (mg/dL) + 0.8 × (4.0 - albumin (g/dL)).

Toxicity grading for calcium will be applied based on the corrected values.

Estimated GFR

The Cockcroft-Gault (CG) formula will be used to calculate eGFR_{CG}:

- eGFR_{CG} (mL/min) = [(140 - age (yrs)) × weight (kg) × (0.85 if female)] / (SCr (mg/dL) × 72), where weight is total body mass in kilograms, and SCr is serum creatinine.

7.2.2. Graded Laboratory Values

The Gilead Grading Scale for Severity of Adverse Events and Laboratory Abnormalities will be used for assigning toxicity grades (0 to 4) to laboratory results for analysis. Grade 0 includes all values that do not meet the criteria for an abnormality of at least Grade 1. For laboratory tests with criteria for both increased and decreased levels, analyses for each direction (ie, increased, decreased) will be presented separately.

If there is any laboratory toxicity grading scale overlapping with the normal reference ranges (eg, grade 1 scale overlaps with normal reference ranges), laboratory values that are within the normal range will be grade 0 except for lipid tests.

For triglycerides, LDL, and cholesterol, the protocol specified toxicity grading scale is for fasting test values, so non-fasting lipid results (or lipid results without known fasting status) will not be graded or summarized by toxicity grades.

7.2.2.1. Treatment-Emergent Laboratory Abnormalities

Treatment-emergent laboratory abnormalities are defined as values that increase at least 1 toxicity grade from baseline at any postbaseline time point, up to the cutoffs specified at the start of Section 7.2.

If the relevant baseline laboratory value is missing, any abnormality of at least Grade 1 observed within the time frame specified above will be considered treatment emergent.

Fasting glucose and nonfasting glucose (including glucose results without a known fasting status) are graded based on different grading scales as specified in the protocol. Most participants had a nonfasting glucose at the Screening visit and a fasting glucose at the Day 1 visit; therefore, both a baseline nonfasting glucose and a baseline fasting glucose are available for most participants, and treatment-emergent laboratory abnormalities will be summarized for both nonfasting glucose and fasting glucose.

Both urine RBC based on microscopic examination, labeled as Hematuria (Quantitative), and urine blood based on a dipstick, labeled as Hematuria (Dipstick), are assessed and assigned a toxicity grade in this study. Hematuria (Quantitative) is a reflex test. Urine RBC based on microscopic examination or Dipstick will be presented in laboratory toxicity summary tables and listings.

7.2.2.2. Summaries of Laboratory Abnormalities

The following summaries (number and percentage of participants) for treatment-emergent laboratory abnormalities will be provided by lab test and treatment group (B/F/TAF, Delayed Switch to B/F/TAF, and All B/F/TAF); participants will be categorized according to the most severe postbaseline abnormality grade for a given lab test:

- Treatment-emergent laboratory abnormalities
- Treatment-emergent Grade 3 and 4 laboratory abnormalities

For all summaries of laboratory abnormalities, the denominator is the number of participants with any nonmissing postbaseline values for the particular laboratory test.

A by-subject listing of all treatment-emergent laboratory abnormalities and treatment-emergent Grade 3 or 4 laboratory abnormalities will be provided by subject ID number and visit in chronological order.

7.2.3. Metabolic Laboratory Evaluations

For metabolic assessments, including fasting glucose and the lipid panel (ie, total cholesterol, triglycerides, LDL, HDL, total cholesterol to HDL ratio); only those measurements under fasting status will be summarized for the B/F/TAF and Delayed Switch to B/F/TAF groups.

In addition, the number and percentage of participants who took lipid modifying medications at baseline and initiated the medications during the study will be provided for the B/F/TAF and Delayed Switch to B/F/TAF treatment groups.

A lipid modifying medication is defined as a medication with drug class (based on World Health Organization [WHO] Drug ATC2 term) “LIPID MODIFYING AGENTS” and WHO Drug preferred drug name containing the wording of “STATIN”.

A sensitivity analysis of fasting lipid tests will be performed by excluding participants who took lipid modifying medications at baseline or initiated the medications during the study: baseline values, Week 72 values, and changes from baseline at Week 72 will be summarized for the B/F/TAF group using descriptive statistics. Only participants with both baseline and Week 72 values will be included in the analysis. A similar summary at Week 48 will be produced for the Delayed Switch to B/F/TAF group.

Summary of baseline, postbaseline, and change from baseline in fasting metabolic laboratory tests will be repeated within each subgroup of baseline ARV medication (see Section 3.4.2).

Median (Q1, Q3) of change from baseline in fasting metabolic assessments over time will be plotted by treatment group (B/F/TAF and Delayed Switch to B/F/TAF).

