Note: Prothrombin Intl. Normalized Ratio (INR) and Prothrombin Time (PT) were graded based on the protocol defined toxicity grade scale. The results and toxicity grade will be listed in listing, but not be summarized in lab toxicity summary table.

Due to the reflexive nature of the quantitative urine RBC test, results will be combined with the dipstick test of urine blood as described below. General rule is that urine RBC (Quantitative) should always be used first (if available), no matter if it is collected at the same time of Urine Blood (Dipstick) or not. The combined Urine RBC (hematuria, Quantitative or Dipstick) toxicity grade will be used for “Maximum treatment-emergent toxicity grade” summary.

Is Post-BL Urine RBC (Quant.) Result Available?	Is BL Urine RBC (Quant.) Result Available?	Is Post-BL Urine Blood (Dipstick) Result Available?	Is BL Urine Blood (Dipstick) Result Available?	How to Determine Treatment-Emergent Toxicity for “Urine RBC (Hematuria, Quantitative or Dipstick)”
Yes	Yes			Compare post BL Urine RBC (Quant.) toxicity grade to BL Urine RBC (Quant.) toxicity grade. If post BL toxicity is greater than BL toxicity, then treatment emergent
Yes	No			Treatment emergent. Use post BL Urine RBC (Quant.) toxicity grade.
No		Yes	Yes	Compare post BL Urine Blood (Dipstick) toxicity grade to BL Urine Blood (Dipstick) toxicity grade. If post BL toxicity is greater than BL toxicity, then treatment emergent
No		Yes	No	Treatment emergent. Use post BL Urine Blood (Dipstick) toxicity grade.
No		No		Do not count participant in the denominator for “Urine RBC (Hematuria, Quantitative or Dipstick)”

BL Baseline. Quant Quantitative. “ ” means any value can be present (or it can be missing), as it does not affect the classification

14) Concomitant nonstudy drug ARV medications (ie, ARV medications other than study drug that are taken while receiving study drug) will be flagged in “Nonstudy Drug Antiviral Medication” listing. The logic to define concomitant nonstudy drug ARV is similar to concomitant non-ARV Medications (see details in Section 7.4.2)

15) Lipid modifying medication analyses:

- Lipid modifying medication is defined to be the concomitant medication with WHO Drug ATC2 term (drug class) “LIPID MODIFYING AGENTS” and WHO Drug preferred drug name (CMDECOD) contains wording of “STATIN” in the ADCM dataset.

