- Participants who took lipid modifying medications at baseline refer to the participants who have any use of the lipid modifying agents at Study Day 1.
 - a) More specifically, participants with “Lipid Modifying Agent Use at Baseline” include those participants in the B/F/TAF safety analysis set meeting both of the following criteria: 1) any selected CM record with the start date \leq the first dose date, and 2) the end date of the selected CM record \geq the first dose date or the end date of the selected CM record is ongoing

- b) For lipid modifying medications with the start date completely unknown, assume the start date is on or before the first dose date; lipid modifying medication is considered as being taken at baseline if the end date is not prior to the first dose date (ie, the end date is on or after the first dose date, completely unknown, or ongoing).
 - c) Lipid modifying medications with the start date prior to the first dose date and the end date unknown (completely missing) are considered as being taken at baseline (the unknown end date is assumed to be on or after the first dose date).
- Participants who initiated lipid modifying medications during the study are defined as the participants in the B/F/TAF safety analysis set who did not take lipid modifying medications at baseline and met the following criteria: any selected CM record with start date after the first B/F/TAF dose date and on and prior to the last B/F/TAF dose date.
- 16) For figures, if at a visit where n (sample size) for any treatment group < 5, data for that treatment group will not be displayed at that visit in the figure, but all data will be included in the corresponding table summary.
- 17) Vital signs and weight, height, BMI will be in the same listing.
- 18) HIV/HBV and HIV/HCV Coinfection:
- The following table presents the HBV and HCV tests with all possible values. Values that have an asterisk after them denote a “positive” (or “quantifiable” for HBV DNA and HCV RNA) result while all others denote a “negative” result.

Label	LBTESTCD	LBTEST	Possible Values
HBsAg	ATT1	Hep.B Surf.Ag Quant(70)CL	NUMERICAL VALUE or “<0.05” or “>124925.00” (IU/mL)
HBsAg	ATT2	Hep. B Surf. Ag Qual(70) CL	“Repeat reactive, confirmed”*, “Repeat Reactive Unconfirmed”, “Non Reactive”
HBsAb	CNT353	anti Hep B Surface Ag2 Qual	“Positive”*, “Negative”
HBcAb	CNT68	Hepatitis B Core Total	“Positive”*, “Negative”

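### The SAP's definition of a lipid modifying medication captures statins only, so users of other drugs in the class are left out of the usage count and stay in the lipid sensitivity analysis as if untreated

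*SAP*

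**What the plan says.** SAP 7.2.3 defines a lipid modifying medication by two joint conditions: the ATC2 class LIPID MODIFYING AGENTS, and a second test on the name that reads "WHO Drug preferred drug name containing the wording of" and then gives the string STATIN. The programming rule in Appendix 6 item 15 has the same two parts, with the class first and then the requirement that the name "contains wording of “STATIN” in the ADCM dataset".

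The definition feeds two outputs in 7.2.3:

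- A usage count in each of the two groups: "the number and percentage of participants who took lipid modifying medications at baseline and initiated the medications during the study will be provided".
- A sensitivity analysis of fasting lipids, run by "excluding participants who took lipid modifying medications at baseline or initiated the medications during the study". For the B/F/TAF group, "Only participants with both baseline and Week 72 values will be included in the analysis"; the Delayed Switch group gets a similar summary at Week 48.

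Item 15 identifies on-study starters as people not on such a drug at baseline who have "any selected CM record with start date after the first B/F/TAF dose date and on and prior to the last B/F/TAF dose date". The reason for starting plays no part.

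**The concern.** The label says lipid modifying medication, but the rule selects statins. A participant taking another drug in the class (a fibrate or ezetimibe would be the obvious examples; the documents name none) is handled as untreated. The usage count then understates lipid-drug use, and the sensitivity analysis keeps some of the people it was set up to remove. The mismatch matters more because 7.2.3 analyses total cholesterol, triglycerides, LDL, HDL and the total cholesterol to HDL ratio. A statin-only rule is a poor filter for triglycerides and HDL. Protocol 7.6.3 itself foresees triglyceride elevations that are managed medically.

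The final analysis has no concurrent comparator. SAP 2.2 leaves the first 24 weeks of the SBR group out of the summaries, so any drug-induced shift in mean change from baseline goes directly into the reported figure.

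**Working it through.** **1. The rule as written.** Counted = (class is LIPID MODIFYING AGENTS) AND (name contains STATIN).

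- In the class, STATIN in the name: counted, participant excluded.
- In the class, no STATIN in the name: not counted, participant stays in.
- Outside the class, STATIN in the name: not counted.

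The third line shows that the class condition alone already screens out similarly named drugs from other classes. Deleting the name condition would not let them in.

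**2. Who is affected.** The set is limited to participants with paired values. Week 72 on B/F/TAF is reached only in the optional extension, which ends early for anyone who gains access to B/F/TAF (Protocol 3.4 and 6.6.1). For Delayed Switch, study days run from the first B/F/TAF dose (SAP 3.8.1), so Week 48 falls at about study Week 24 + 48 = 72, also in the extension. Neither planned arm size (320 or 160) is the right denominator, and the documents do not give the right one.

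**3. Illustrative size of the definition problem.** The plan states no figure to reproduce. Shift in mean change = −q × e, where q is the share of the set that starts a non-statin drug in the class and e is its effect on LDL. Both are assumed.

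- q = 1%: e = 20 gives −0.2 mg/dL; e = 40 gives −0.4.
- q = 3%: e = 20 gives −0.6 mg/dL; e = 40 gives −1.2.

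A participant on a stable non-statin drug throughout has treated values at both ends. That affects the reported levels more than the change.

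**4. The conditional point on starters.** Let p be the share starting a counted drug, SD the standard deviation of the untreated LDL change, and ρ the correlation between starting and that change. Dropping starters shifts the mean by −SD × ρ × φ(c)/(1 − p), with c the normal quantile at 1 − p. With SD = 25 mg/dL (assumed):

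- ρ = 0: no shift at any p.
- ρ = 0.3: −0.4, −0.8 and −1.5 mg/dL at p = 2%, 5% and 10%.
- ρ = 0.6: −0.7, −1.6 and −2.9 mg/dL at the same p. At 5%, c = 1.645 and φ(c) = 0.103, so 25 × 0.6 × 0.103/0.95 = 1.6.

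The main fasting summary keeps starters' on-drug values. Its shift is −p × e: for e = 20 to 40 and p = 2% to 10%, −0.4 to −4.0 mg/dL.

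**The case against.** **Other outputs show the drugs and the starters.** SAP 7.4.2 tabulates concomitant non-ARV medications by group and preferred drug name and lists the participants taking them, so each non-statin lipid drug appears by name. This stands as a mitigation. What is still lost is the class total and the split between baseline users and starters, and the sensitivity set stays uncorrected. Starters remain in the main fasting summary, and graded abnormalities use the most severe post-baseline result (SAP 7.2.2.2 and Appendix 6 item 12), so a graded rise measured before treatment is kept.

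**A stronger reading does not hold.** A reader might infer that the exclusion removes people whose lipids rose enough to need treatment, and hence that both summaries do understate a rise. The documents do not support this as fact. Starters are identified by date alone, and if starting is unrelated to the lipid change, dropping them causes no bias.

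Nor is dropping starters clearly worse than keeping them. Assume 5% start after a 30 to 40 mg/dL rise, the drug lowers LDL by 20 to 40, and everyone else has zero change. Starters' observed change then lies between 30 − 40 = −10 and 40 − 20 = +20. Removing them moves the mean by +0.5 to −1.0 mg/dL relative to the main summary, so even the direction is not fixed.

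**A headcount is also tempting.** Assuming 2% to 5% non-statin use and applying it to 320 gives 6 to 16 participants. The rate is not in the documents, and 320 ignores the paired-value requirement.

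**Conclusion.** The definition point holds on the text alone: in both places the rule is narrower than its label, and both the usage count and the sensitivity analysis inherit the gap. Its size cannot be determined from the documents. The −0.2 to −1.2 mg/dL range rests wholly on assumed use and drug effect.

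The starter point holds only conditionally. If people started treatment because their lipids rose, excluding them and using their on-drug values both lean toward a smaller rise, and agreement between the two summaries is then weak reassurance. Without that condition, excluding starters introduces no bias.

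This is a minor matter in a descriptive safety analysis. The sensitivity analysis still removes baseline statin users and statin-treated follow-up values, so it would be wrong to say that it fails its purpose altogether.

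**What to change.** Delete the STATIN condition in SAP 7.2.3 and in Appendix 6 item 15, so that the ATC2 class, or a reviewed list of drugs within it, defines the medication. This is one line in each place. SAP section 1 already provides for documenting changes made after finalization in the clinical study report. The cost is a somewhat smaller sensitivity set, and drugs in the class with weak lipid effects would also count; a reviewed list limits the latter.

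Optionally, add a summary that excludes only baseline users and takes starters' fasting values up to the start of the drug. Do not simply carry the last pre-drug value forward for everyone. Fasting lipids are scheduled only at Day 1 and Weeks 24, 48 and 72 (Protocol 6.9.1), so a B/F/TAF participant who starts a drug before Week 24 would normally have only the Day 1 value and would be given a change of zero, which itself leans toward no effect. Report starters with no on-treatment value before the drug separately. The added cost is a small derivation from drug start dates that item 15 already uses.

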3.4.2. Subject Subgroups for Safety Analyses

- 1) Incidence of all treatment-emergent AEs (TEAEs) will be analyzed for the following subject subgroups (also see Section 7.1.6):
 - Age (years): (a) < 50 and (b) ≥ 50
 - Sex at birth: (a) male and (b) female
- 2) Renal-related laboratory tests (ie, serum creatinine and eGFR_{CG}) will be analyzed for the following subgroups:
 - Baseline ARV Medication containing any of the following: rilpivirine (RPV), dolutegravir (DTG), ritonavir (RTV), cobicistat
 - Baseline ARV Medication not containing any of the following: RPV, DTG, RTV, cobicistat

3) Fasting metabolic laboratory tests will be analyzed for the following subgroups:

- Baseline ARV Medication containing TAF
- Baseline ARV Medication containing TDF
- Baseline ARV Medication not containing any of the following: TAF, TDF
- Baseline ARV Medication containing efavirenz (EFV)
- Baseline ARV Medication not containing EFV

4) Selected safety endpoints may be analyzed for the following subject subgroups (see Section 8.1 for details):

- Participants with HIV/HBV coinfection at baseline
- Participants with incident HIV/HBV coinfection while on study drug (if any)

5) Selected safety endpoints will be analyzed for the following subject subgroups (see Section 8.2 for details):

- Participants with HIV/HCV coinfection at baseline
- Participants with incident HIV/HCV coinfection while on study drug (if any)

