3.8. Analysis Windows

3.8.1. Definition of Study Day

Study Day 1/First Dose Date is defined as the day when the first dose of B/F/TAF was taken. The first dose date is the earliest nonmissing start date of B/F/TAF study drug recorded on the Study Drug Administration eCRF.

Study Days are calculated relative to Study Day 1. For events that occur on or after the Study Day 1 date, study days are calculated as (visit date minus Study Day 1 date plus 1). For events that occurred prior to Study Day 1, study days are calculated as (visit date minus Study Day 1 date).

Last Dose Date is defined as the maximum, nonmissing end date of B/F/TAF recorded on the Study Drug Administration eCRF and “Study Drug Permanently Discontinued” box checked for participants who prematurely discontinued study drug or completed study drug according to the Study Drug Completion eCRF.

For partial or missing last dose dates, please refer to the programming specifications for imputation rule details.

Last Study Date is the latest of the study drug start dates and end dates, the clinic visit dates, and the laboratory visit dates, including the 30-day follow-up visit date, for participants who prematurely discontinued study according to the Study Completion eCRF.

Baseline value is defined as the last value obtained on or prior to Study Day 1 for all assessments.

Note: for first dose date for SBR treatment group for listings, refer to the Week 48 SAP.

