3.8.2. Analysis Windows

Participant visits might not occur on protocol specified days. Therefore, for the purpose of analysis, observations will be assigned to analysis windows.

The analysis windows for HIV-1 RNA, hematology, chemistry, urinalysis, urine pregnancy laboratory tests, eGFR_{CG}, vital signs, and weight are presented in [Table 3-1](#).

[figure not shown]
Table 3-1. Analysis Windows for HIV-1 RNA, Hematology, Chemistry, Urinalysis, Urine Pregnancy Laboratory Tests, eGFR_{CG}, Vital Signs and Weight

Visit ID	Nominal Day	Lower Limit	Upper Limit
Baseline			1
Week 4	28	2	56
Week 12	84	57	126
Week 24	168	127	210
Week 36	252	211	294
Week 48	336	295	378
Week 60	420	379	462
Week 72	504	463	546
Week 84	588	547	630

The analysis windows for CD4+ cell count, CD4 %, and metabolic assessments (including fasting glucose and lipid panel: total cholesterol, high density lipoprotein [HDL], direct low density lipoprotein [LDL], triglycerides, and total cholesterol to HDL ratio are presented in [Table 3-2](#).

Table 3-2. Analysis Windows for CD4+ cell count, CD4 %, and Metabolic Assessments

Visit ID	Nominal Day	Lower Limit	Upper Limit
Baseline	1		1
Week 24	168	2	252
Week 48	336	253	420

The analysis windows for plasma HBV DNA are presented in [Table 3-3](#).

Table 3-3. Analysis Windows for Plasma HBV DNA

Visit ID	Nominal Day	Lower Limit	Upper Limit
Baseline	1		1
Week 24	168	2	252
Week 48	336	253	420

3.8.3. Selection of Data in the Event of Multiple Records in an Analysis Window

Depending on the statistical analysis method, single values are required for each analysis window. For example, change from baseline by visit usually requires a single value, whereas a time to event analysis would not require one value per analysis window. When a single value is needed, the following rule(s) will be used.

If multiple nonmissing numeric observations exist in a window, then records will be chosen as follows:

- For baseline, the latest available record on or prior to the first dose date of study drug will be selected. If there are multiple records with the same time or no time recorded on the same day, average will be used for the baseline value, except for HIV-1 RNA (see below).
- For postbaseline visits:

For CD4+ cell count, CD4%, and HBV DNA, the record(s) collected on the latest day in the window will be selected for analysis.

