- n Chemistry profile: alkaline phosphatase, AST, ALT, total bilirubin, direct and indirect bilirubin, total protein, albumin, CPK, bicarbonate, BUN, calcium, chloride, creatinine, glucose, phosphorus, magnesium, potassium, sodium, amylase, and Cystatin C. After Day 1, calcium, phosphorous, magnesium, and amylase (reflex lipase testing is performed in participants with total amylase $> 1.5 \times$ ULN) will not be collected. Analyses of glucose will be done as part of the fasting metabolic assessments, and not as part of the chemistry profile at Day 1, Weeks 24, 48, and 72. Cystatin C will only be collected at Day 1.
- o Metabolic Assessments will be performed at Day 1, Weeks 24, 48, and 72. Fasting (no food or drinks, except water, at least 8 hours prior to blood collection) glucose and lipid panel (total cholesterol, HDL, direct LDL, triglycerides). If the participant has not fasted prior to the visit, the visit may proceed, but the participant must return within 72 hours in a fasted state to draw blood for the metabolic assessments.
- p CBC with differential and platelet count.
- q HIV 1 genotype and phenotype testing for participants with confirmed virologic failure and HIV 1 RNA >200 copies/mL. Following virologic rebound, participants will be asked to return to the clinic (2-3 weeks later) prior to the next scheduled visit or at the next scheduled study visit for a HIV 1 RNA and HIV 1 resistance analysis (reverse transcriptase, protease, and integrase genotype and phenotype) blood draw. Based on the results of this testing, participants should be managed according to the Virologic Rebound Schema.
- r [REDACTED]
- s HBV blood panel will be performed at Screening and Week 48: HBsAg, HBsAb, HBcAb.
- t **For participants who are HBV co-infected (defined in Protocol Section 6.9.1):** The following HBV Blood panel will be conducted by the central laboratory: HBsAb, HBsAg (qualitative and quantitative), and HBeAg (if negative, reflex HBeAb).
For participants who are NOT HBV co-infected: The following HBV Blood panel will be conducted by the central laboratory: HBsAb, HBcAb, and HBsAg. Participants who are HBsAg or HBcAb positive will have a reflex test for HBV DNA (viral load).
- u **For participants who are HBV co-infected:** Plasma HBV DNA will be collected at Day 1, Week 24, Week 48 and ESDD.
- v Hepatitis C virus serology will be performed at Screening, Week 48, and Week 72. Participants who are HCVAb positive will have an HCV RNA test performed.

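### SAP Table 3-2 has no Week 72 window for fasting lipids, so the Week 72 lipid sensitivity analysis required in SAP 7.2.3 has no eligible participants

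*SAP*

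**What the plan says.** SAP 7.2.3 calls for a sensitivity analysis of fasting lipids that leaves out users of lipid-modifying medication. For the immediate-switch group the timepoint is Week 72: "baseline values, Week 72 values, and changes from baseline at Week 72 will be summarized for the B/F/TAF group using descriptive statistics". Entry is restricted: "Only participants with both baseline and Week 72 values will be included in the analysis". The Delayed Switch group gets a similar summary at Week 48.

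SAP 3.8.2 explains how a visit value arises. Because visits may not fall on the planned day, "Therefore, for the purpose of analysis, observations will be assigned to analysis windows". Fasting glucose and each lipid are named there and sent to "Table 3-2. Analysis Windows for CD4+ cell count, CD4 %, and Metabolic Assessments". That table has three rows: Baseline, Week 24 (nominal Day 168, Days 2 to 252) and Week 48 (nominal Day 336, Days 253 to 420). A Week 72 window (nominal Day 504, Days 463 to 546) appears only in Table 3-1, which covers other assessments.

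The samples are scheduled. SAP Appendix 1, footnote o, states: "Metabolic Assessments will be performed at Day 1, Weeks 24, 48, and 72". Protocol 6.9.1 gives the same schedule.

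**The concern.** One rule in the SAP empties an analysis that another section of the same SAP requires. With no Week 72 window for lipids, no record can become a Week 72 lipid value, and the inclusion rule in 7.2.3 then excludes everyone.

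The gap reaches further than that one table. SAP 7.2.1 defines the routine summaries by window ("Change from baseline at each postbaseline analysis window"), and SAP 3.4.2, item 3, repeats them by baseline regimen ("Fasting metabolic laboratory tests will be analyzed for the following subgroups"). For the immediate-switch group, the continuous lipid and glucose results in these summaries, and in the median-change plots of 7.2.3, would end at Week 48. Week 72 is that group's longest scheduled fasting follow-up.

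A programmer who meets the gap must either produce an empty table or choose a window that the plan does not specify.

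**Working it through.** **Inputs**
- Table 3-2 (SAP 3.8.2): Week 24 = Days 2 to 252; Week 48 = Days 253 to 420; no later row.
- Table 3-1 (SAP 3.8.2): Week 72 = nominal Day 504, Days 463 to 546; not for metabolic assessments.
- Visit tolerance of 6 days either way (SAP Appendix 1, footnote c). A participant who has not fasted returns within 72 hours (footnote o).
- Day origin (SAP 3.8.1): "Study Day 1/First Dose Date is defined as the day when the first dose of B/F/TAF was taken".
- Protocol 6.4 allows the first dose to be taken the day after the Day 1 visit.

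**Reproducing the plan's limits.** Take each upper limit as the midpoint between consecutive nominal days.
- Table 3-2, Week 24: (168 + 336)/2 = 252, as stated.
- Table 3-2, Week 48, with Week 72 as the next visit: (336 + 504)/2 = 420, as stated.
- The same rule reproduces all eight post-baseline rows of Table 3-1.

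**Immediate-switch group**
- Nominal day: 72 × 7 = 504.
- Visit tolerance: 504 − 6 = 498 to 504 + 6 = 510. With the fasted return, up to 510 + 3 = 513.
- Distance past the last limit: 498 − 420 = 78 days, or 77 if the first dose came the day after the visit.
- Of the 16 days from 498 to 513, none lies in any Table 3-2 window.
- Week 72 is one of three scheduled post-baseline fasting draws (Weeks 24, 48 and 72).

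**Delayed Switch group**
- Days are counted from the first B/F/TAF dose at study Week 24, so study Week 72 is (72 − 24) × 7 = 336.
- With 6 days' tolerance at both visits: 336 − 12 = 324 to 336 + 12 = 348, or 351 with the fasted return.
- All of these lie inside 253 to 420, so this group's Week 48 summary works.

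**Subgroups affected (SAP 3.4.2, item 3).** TAF; TDF; neither TAF nor TDF; EFV; no EFV: five in all.

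**With a Week 72 row added**
- Lower limit: 420 + 1 = 421.
- Upper limit under the same 168-day spacing: (504 + 672)/2 = 588.
- All days from 498 to 513 then map to Week 72, and the existing rows do not change.

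**The case against.** The strongest reply is that the intent is plain. SAP 7.2.3 names the timepoint, group, statistics and inclusion rule, the draw is scheduled, and Table 3-1 already gives a Week 72 window for chemistry. Appendix 6, item 13, lists fasting lipids and glucose under the chemistry battery. In practice someone would raise a query or borrow that window, and an empty table is unlikely to be published. That may well be so. But SAP 3.8.2 assigns these tests by name to Table 3-2, and nothing authorises the Table 3-1 window or the nominal visit label in its place. The improvised choices also differ: Table 3-1 starts at Day 463, whereas Table 3-2's own spacing would start at Day 421.

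A second reply is that only the sensitivity analysis is contradicted. The by-window summaries, subgroup summaries and plots comply with the SAP even if they stop at Week 48. This is right as a matter of wording: for those outputs the loss of Week 72 is a consequence of the gap, not a separate contradiction.

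A third is that the limit of 420 does not prove that a row was left out. Table 3-3 ends at the same day, although HBV DNA is not scheduled at Week 72, and 420 is also simply 336 + 84. This stands as well. The finding does not depend on why the row is absent.

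**Conclusion.** The concern holds. Under the SAP's windowing rule, the Week 72 lipid sensitivity analysis for the immediate-switch group has N = 0, and every on-schedule Week 72 fasting draw in that group lies at least 77 days beyond the last metabolic window. This rests on applying SAP 3.8.2 literally.

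The number of participants involved is not given. It is at most the 320 planned, less those who stop early, do not enter the extension or leave it once they have access to B/F/TAF. For the sensitivity analysis, users of lipid-modifying medication are also excluded.

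The consequences are confined to descriptive safety output. The values remain in the listings (SAP 7.2) and in the toxicity-grade summaries, which Appendix 6, item 12, does not limit to by-visit records. The primary and secondary efficacy endpoints are unaffected. The defect should be corrected, but it does not threaten the trial's conclusions.

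**What to change.** Add one row to Table 3-2 for metabolic assessments: Week 72, nominal Day 504, Days 421 to 588. The lower limit follows from the existing Week 48 row. The upper limit is an assumption, because dosing ends at Week 72 and no later fasting draw is scheduled. The 546 used in Table 3-1 would capture the same on-schedule draws. Either is acceptable if stated in advance.

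Table 3-2 also governs CD4+ count and CD4 percentage, which Protocol 6.9.1 schedules at Week 72 too. The SAP's efficacy text is partly redacted, so whether CD4 needs the row cannot be judged here. The new row should say which assessments it covers.

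If the SAP is already final, record the change in the clinical study report, as SAP Section 1 provides. The cost is one table row or one documented change, with no new data collection.
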